- b. The starting dose of lenalidomide is 15 mg QD and the final dose for the expansion portion of the study will be determined based on the outcome of the DLT review. Subjects will receive lenalidomide at the assigned dose or the final dose for up to 12 cycles or until disease progression or intolerance, whichever comes first.

Acalabrutinib has been used in combination with rituximab at the doses mentioned above and this combination has an acceptable safety profile (current version of Acalabrutinib Investigator Brochure). There will be an inter-subject dose escalation or de-escalation during the DLT review period to find the appropriate dose of lenalidomide that can be used in combination with acalabrutinib and rituximab.

DLT review and enrollment are presented in Figure 3 and will be conducted as follows (DLT criteria are defined in Section 3.5.5):

Expand cohort Lenalidomide 20 mg QD Rolling DLT < 2/6 DLT *Inter-subject Dose Escalation for subjects N = 14without toxicity review Lenalidomide Rolling DLT 20 mg QD review < 2/6 DLT *N=6 ≥ 2 DLT Expand cohort Lenalidomide Lenalidomide 15 15 mg QD mg QD *N=6 N=14 Rolling DLT Expand cohort review Lenalidomide 10 mg QD < 2/6 DLT N=14 ≥ 2 DLT Lenalidomide 10 mg QD N=6 **Acalabrutinib dose will not be reduced unless specific toxicity ≥2DLT clearly attributable to acalabrutinib occurs. No dose reduction for STOP rituximab per label

Figure 3 Dose-Limiting Toxicity Review and Enrollment for Part 3

 $\label{eq:decomposition} \mbox{DLT=dose-limiting toxicity; QD=once per day}.$

Six subjects are planned to be enrolled initially and treated with acalabrutinib, rituximab, and lenalidomide (15 mg PO QD) in Cycle 1. At the end of the cycle, subjects will be evaluated for DLTs on a rolling basis (Figure 3).

- If there are ≥2 subjects with DLTs on 15 mg of lenalidomide QD, the dose of lenalidomide will be reduced to 10 mg QD, and 6 more subjects are planned to be enrolled at this reduced dose of lenalidomide.
 - If there are ≥2 subjects with DLTs at the end of Cycle 1 on 10 mg lenalidomide QD, enrollment will close.
 - If there are <2 of 6 subjects with DLTs, then approximately 14 additional subjects will be enrolled and treated with lenalidomide 10 mg QD for Cycles 1 through 12.
- If there are <2 of 6 subjects with DLTs on 15 mg QD, 6 additional subjects are planned to be enrolled to receive an increased dose of lenalidomide at 20 mg QD.

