 - If there are ≥2 subjects with DLTs, the dose of lenalidomide will be reduced back to 15 mg QD. Approximately 14 more subjects will be added to complete enrollment at the 15-mg QD dose.
 - If there are <2 of 6 subjects with DLTs, 20 mg of lenalidomide will be the dose used for Cycles 2 through 12. Approximately 14 more subjects will be added to complete enrollment.

Note: Subjects will be evaluated for DLTs at the end of the first cycle, on a rolling basis, when they complete a cycle of treatment.

Refer to Appendix 6 for a comprehensive list of study assessments and their timing.

Part 4

At the time of Amendment 6, the sponsor made the decision to close Part 4 cohort to enrollment. Therefore, Part 4 has been removed.

All Parts

Twenty-eight days of study drug administration is 1 cycle. Treatment with acalabrutinib may be continued until confirmed disease progression or an unacceptable drug-related toxicity occurs.

Dose modification provisions are provided in Section 3.5.7. Note: Temporary withholding of acalabrutinib for as little as 7 days can cause a transient worsening of disease and/or of constitutional symptoms. All subjects who discontinue study drug

will have a safety follow-up visit 30 (+7) days after the last dose of study drug until the final data cut-off regardless of whether the subject receives a new anticancer therapy or demonstrates disease progression within this timeframe.

All subjects will have hematology, serum chemistry, hepatitis serology, and urinalysis safety panels performed at screening. For Part 1 and Part 2, once dosing commences (Day 1), all subjects will be evaluated for safety, including hematology and serum chemistry, once weekly for the first 4 weeks, every 2 weeks in Cycle 2, monthly through Cycle 13, and then every 3 months thereafter. For Part 3, once dosing commences (Day 1), all subjects will be evaluated for safety, including hematology and serum chemistry, once weekly for the first 4 weeks, every 2 weeks in Cycle 2, and monthly through Cycle 13, and for Part 3, every 8 weeks starting Cycle 14 up to Cycle 28 (rituximab infusion ends at Cycle 26) and every 3 months thereafter.

Part 3

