3.4.7 Replacement of Subjects

Part 1 and Part 2

Any subject who does not complete Cycle 2 may be replaced at the discretion of the study investigator and sponsor. Should the decision be made to replace a subject, the replacement subject will be assigned to the same treatment combination regimen as the original subject.

Part 3

Any subject who does not complete study therapy through Cycle 1 for reasons other than the occurrence of a DLT may be replaced at the discretion of the study investigator and sponsor. Should the decision be made to replace a subject, the replacement

subject will be assigned to the same treatment combination regimen as the original subject.

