3.5.3 Administration of Study Drug

Investigators are prohibited from supplying acalabrutinib to any subjects not properly enrolled in this study. The investigator must ensure that subjects receive acalabrutinib only from personnel who fully understand the procedures for administering the drug.

Acalabrutinib is intended to be administered orally with 8 ounces (approximately 240 mL) of water. Acalabrutinib taken with an acidic beverage may impact exposure to acalabrutinib (refer to the current Acalabrutinib Investigator brochure). Acalabrutinib may be administered without regard to food. The capsules or tablets should be swallowed intact and subjects should not attempt to open capsules or crush tablets, and both formulations should not be dissolved in water.

Acalabrutinib should be taken BID, approximately 12 hours apart. Dietary restrictions are provided in Section 3.7.4.

If a dose is missed, it can be taken within 3 hours after the scheduled time with a return to the normal schedule with the following dose. If the time from the scheduled time of

administration has been >3 hours, the dose should not be taken, and the subject should take the next dose. The missed dose will not be made up and must be returned to the site at the next scheduled visit.

Rituximab is to be administered as an IV infusion, not an IV push or bolus. Detailed instructions for the preparation and administration of rituximab are provided in the Rituxan/MabThera package insert and per institutional standards. No dose reductions for rituximab are allowed. On days when both acalabrutinib and rituximab are administered, the rituximab infusion should begin approximately 1 hour after the acalabrutinib dose.

Subjects will continue on acalabratinib after completion of rituximab treatment or may do so if rituximab is discontinued due to intolerability at any time in the study.

Lenalidomide is to be administered orally at approximately the same time each day, either with or without food. The capsules should be swallowed whole with water. The capsules should not be opened, broken, or chewed. Lenalidomide is administered for the first 21 days of each 28-day cycle. On days that both acalabrutinib and lenalidomide are administered, lenalidomide should be taken approximately 30 minutes prior to the first daily dose of acalabrutinib. Dose modification provisions are provided in Section 3.5.7.

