3.5.5 Definition of Dose-limiting Toxicity (Part 3)

A DLT will be defined as the occurrence of any of the following study drug-related AEs

during the DLT review period. (Note: AEs clearly related to disease progression or the subject's medical history and associated comorbidities considered by the investigator to be unrelated to study drugs, will not be considered DLTs. Infusion reactions clearly associated with rituximab infusion will not be considered DLTs.):

- 1. Non-hematologic DLTs include:
 - a) Grades 3 or 4 nausea, vomiting, or diarrhea lasting >7 days despite optimal antiemetic or antidiarrhea management or any Grade 3 or Grade 4 toxicity
 - b) Any grade Stevens-Johnson syndrome or toxic epidermal necrolysis
 - c) AST or ALT >3 × ULN concurrently with total bilirubin >2 × ULN
 - d) Clinical TLS not resolving to baseline after a 2-week treatment delay
- Exceptions are deep vein thrombosis (DVT), correctable electrolyte
 abnormalities, or Grade 3 or Grade 4 laboratory abnormalities lasting ≤7 days;
 Grades 3 or 4 fatigue, anorexia, non-neutropenic fever, Grade 3 rash resolving to
 Grade 2 within 10 days (allowed therapy with steroids)
- 2. Hematologic DLTs include:
 - a) Grade 3 or Grade 4 neutropenia with fever ≥38.5°C or infection, or Grade 4 neutropenia lasting >7 days despite adequate granulocyte-colony stimulating factors (G-CSF) use
 - b) Grade 3 or Grade 4 thrombocytopenia with hemorrhage. If thrombocytopenia improves to Grade ≤2 or to ≥80% of the baseline value within 28 days, without a platelet transfusion, this will not be considered a DLT
 - c) Any Grade 4 hematologic toxicity unrelated to the underlying disease
- 3. Any study drug-related Grade 5 AE
- 4. Any study drug-related toxicity leading to an individual drug dose delay of >21 consecutive days for acalabrutinib or >14 consecutive days for lenalidomide will be considered as a DLT. Subjects should receive at least one dose of rituximab in Cycle 1 to be evaluable for a DLT.

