#### 5. ANALYSIS POPULATIONS

#### **5.1 All-Treated Population**

The all-treated population is defined as all subjects who receive ≥1 dose of any study drug (acalabrutinib, rituximab, or lenalidomide). Demographic and baseline characteristics, efficacy analyses, and safety analyses will be performed on the all-treated population unless otherwise specified.

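### DLT evaluability in Part 3 is explicitly tied to one rituximab dose and sets no minimum exposure to lenalidomide, so the 2-of-6 rule can count under-exposed subjects as DLT-free

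*Protocol*

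**What the plan says.** Part 3 uses an inter-subject escalation to "find the appropriate dose of lenalidomide that can be used in combination with acalabrutinib and rituximab" (Protocol 3.1). Acalabrutinib and rituximab start at fixed doses. Six subjects begin at lenalidomide 15 mg, and two rules then lead upward:

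- "If there are <2 of 6 subjects with DLTs on 15 mg QD, 6 additional subjects are planned to be enrolled" at 20 mg.
- At 20 mg: "If there are <2 of 6 subjects with DLTs, 20 mg of lenalidomide will be the dose used for Cycles 2 through 12", with about 14 more subjects added.

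Four provisions bear on who counts in the six:

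- Protocol 3.5.5: "Subjects should receive at least one dose of rituximab in Cycle 1 to be evaluable for a DLT".
- Protocol 3.5.5, item 4: a study-drug-related toxicity is a DLT if it delays acalabrutinib by more than 21 consecutive days, and a delay of ">14 consecutive days for lenalidomide will be considered as a DLT".
- Protocol 3.1 (note): DLTs are reviewed at the end of Cycle 1, once the subject has completed a cycle.
- Protocol 3.4.7: a Part 3 subject who does not complete Cycle 1 therapy for a reason other than a DLT "may be replaced at the discretion of the study investigator and sponsor".

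SAP Section 5 defines three populations: all-treated, efficacy-evaluable and PK. For the first, "The all-treated population is defined as all subjects who receive ≥1 dose of any study drug". There is no DLT-evaluable set, and the adverse event outputs listed in SAP 7.7.1 include no DLT table.

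**The concern.** A dose-finding rule that counts DLTs among six subjects is informative only if all six were exposed to the drug being escalated for long enough to show its toxicity. Here the one explicit condition is a dose of rituximab, which every subject is due on Day 1 and whose dose does not vary. A subject who received little lenalidomide can meet it, have no DLT, and enter the count as evidence that the dose is tolerable.

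The error runs in one direction. Under-exposure can only lower a subject's chance of a DLT, so counting such subjects makes it more likely that a dose is cleared. The consequence is the dose given to the expansion subjects and the dose reported as tolerable in a part whose primary objective is safety.

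**Working it through.** **1. What the provisions leave open.** Planned dosing: "Lenalidomide is administered for the first 21 days of each 28-day cycle" (Protocol 3.5.3), so 21 doses in Cycle 1. Three kinds of subject can be under-exposed without having a DLT.

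- *Non-toxicity stop.* Item 4 applies only to drug-related toxicity, so it does not reach this subject. Section 3.4.7 permits replacement but does not require it, and does not say that the subject drops out of the six.
- *Toxicity hold of 14 days or less.* A hold on Days 4 to 17 lasts 17 − 4 + 1 = 14 days, which is not more than 14. Doses taken are Days 1–3 and 18–21: 3 + 4 = 7 of 21, or 33%. The subject reaches the end of Cycle 1 on treatment.
- *Table 3 interruption that is not a DLT.* Table 3 interrupts lenalidomide for ANC below 1.0 × 10⁹/L for 7 days and resumes it 5 mg lower. Section 3.5.7 places Grade 4 at ANC below 500/µL, which is 0.5 × 10⁹/L. A subject between 0.5 and 1.0 without fever or infection therefore meets no hematologic DLT criterion. Likewise, Grade 3 rash improving to Grade 2 within 10 days is excepted from the DLTs, while Table 3 holds lenalidomide for a related Grade 3 toxicity and restarts it at the next lower dose. In both cases a subject assigned 20 mg may take 15 mg for the rest of Cycle 1 and still count as DLT-free at 20 mg.

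**2. Size.** Neither document states an operating characteristic for the rule, so there is no figure to reproduce. The true DLT rate p and the number of under-exposed subjects k are my assumptions.

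A dose is cleared when fewer than two of six have a DLT. With no residual risk in the under-exposed, only m = 6 − k subjects can have one:

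P(cleared) = (1 − p)^m + m·p·(1 − p)^(m−1)

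At p = 1/3:

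- m = 6: 64/729 + 192/729 = 256/729 = 35.1%
- m = 5: 32/243 + 80/243 = 112/243 = 46.1%
- m = 4: 16/81 + 32/81 = 48/81 = 59.3%

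If under-exposed subjects keep one third of the risk, each has DLT probability 1/9:

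- k = 1: (112/243)(8/9) + (32/243)(1/9) = 928/2187 = 42.4%
- k = 2: (48/81)(64/81) + (16/81)(16/81) = 3328/6561 = 50.7%

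The same calculation over a range of rates (lower figure: one third of the risk kept; upper figure: none kept):

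| Assumed true DLT rate | All six exposed | One under-exposed | Two under-exposed |
|---|---|---|---|
| 25% | 53.4% | 60.0–63.3% | 66.9–73.8% |
| 1/3 | 35.1% | 42.4–46.1% | 50.7–59.3% |
| 40% | 23.3% | 30.2–33.7% | 38.7–47.5% |
| 50% | 10.9% | 16.1–18.8% | 23.4–31.2% |

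**The case against.** The strongest reply is that the rituximab sentence adds a condition and does not replace the others. Cycle 1 treatment in Part 3 means all three drugs, and DLTs are assessed on completing the cycle. On an ordinary reading, someone who stopped lenalidomide in the first days has not completed it and can be replaced. Item 4 also catches most early stops for drug-related toxicity, since 21 dosing days leave ample room for more than 14 days off drug.

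Much of this stands. A reader might infer that DLT evaluability rests on one rituximab dose and nothing else; Sections 3.1 and 3.4.7 and item 4 do not support that. But completion is not defined by lenalidomide doses, replacement is optional, and item 4 leaves out the three groups above.

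It is also fair to say that the documents give no basis for expecting one or two under-exposed subjects in six, and that zero residual risk is a worst case. Such subjects had some lenalidomide, may remain on acalabrutinib and rituximab, and a DLT may be related to any study drug. The upper figures are therefore bounds. The one related fact in the protocol is that an ibrutinib-based triplet delivered only 64% of the planned lenalidomide dose intensity (Sections 1.7 and 3.3). That figure is not specific to Cycle 1.

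Two further inferences should be avoided. Nothing says that the SAP's all-treated population is the DLT denominator; the dose decision is a rolling review under the protocol. Nor do the documents show that any dose was in fact cleared on under-exposed subjects.

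Finally, the decision may be past. SAP 7.5.3 computes relative dose intensity against an assigned dose of 15 or 20 mg, which suggests that the 10 mg branch was not taken. That limits the remedy but leaves the reporting need.

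**Conclusion.** The point holds as a gap between three sections. Read together, Protocol 3.1, 3.4.7 and 3.5.5 do not say how much lenalidomide a subject must have received to count among the six, and a subject with little of it can be counted as DLT-free. The effect is toward clearing a dose. At an assumed DLT rate of one third, the chance of clearing rises from 35% to 42–46% with one under-exposed subject and to 51–59% with two. The direction follows from the rule; the size depends on assumed DLT rates, numbers of under-exposed subjects and residual risk, none of which the documents give.

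The planned outputs would not let a reader judge whether this happened. SAP 7.5.3 summarizes lenalidomide exposure, withholding and reduction over the whole treatment period, not for Cycle 1 in the subjects behind each decision.

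**What to change.** Reconcile Protocol 3.1, 3.4.7 and 3.5.5 so that the six are a defined DLT-evaluable set: a subject who had a DLT, or who completed Cycle 1 with a minimum of planned lenalidomide that the sponsor specifies. State that a non-evaluable subject is not counted as DLT-free. No threshold, dose or clinical rule is proposed here.

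Add the set to SAP Section 5, and to Section 7.7 a DLT table by assigned dose level showing the Cycle 1 lenalidomide each subject received.

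If the dose decision has been made, the SAP set and table are the remaining action.

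The cost is wording, one table and possibly a few replacement subjects. Every path to expansion uses 6 + 6 + 14 = 26 subjects, so the stated 26 to 32 leaves up to six places.

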3.5.6 Dose Delays

Study treatment with acalabrutinib, rituximab, lenalidomide (if applicable), or combination treatment should be held for any unmanageable, potentially study drug-related toxicity that is Grade ≥3 in severity. Any other clinically important events where dose delays may be considered appropriate by the investigator must be discussed with the medical monitor. Study drug may be held for a maximum of 28 consecutive days from expected

dose due to toxicity. Study treatment should be discontinued in the event of a toxicity lasting >28 days, unless reviewed and approved by the medical monitor.

Note: Temporary withholding of acalabrutinib for as little as 7 days can cause a transient worsening of disease and/or of constitutional symptoms.

3.5.7 Dose Modification and Discontinuation

All acalabrutinib dose modifications (Table 1 and Table 2) should be discussed with the medical monitor prior to instituting changes. For toxicities that are common to both acalabrutinib and lenalidomide, consider adjusting the dose of lenalidomide before adjusting the dose of acalabrutinib per the recommendations below:

- Grade 4 neutrophil count decreases (ANC <500/µL) for >7 days (hematopoietic colony-stimulating factors are permitted per American Society of Clinical Oncology [ASCO] guidelines] and use must be recorded on the electronic case report form [eCRF])
- Grade 3 platelet count decreases in the presence of significant bleeding
- Grade 4 platelet count decreases
- Grade 3 or 4 nausea, vomiting, or diarrhea, if persistent despite optimal antiemetic and/or antidiarrheal therapy
- Any other Grade 4 toxicity or unmanageable Grade 3 toxicity

Table 1 Drug Modification and Discontinuation Actions for Acalabrutinib (in Combination with Lenalidomide)

Occurrence	Action
1st–2nd	Hold acalabrutinib until recovery to Grade ≤2 or baseline; may restart at
100 2110	original dose level (100 mg BID)
3rd	Hold acalabrutinib until recovery to Grade ≤2 or baseline; restart at 100 mg
ord	once daily
4th	Discontinue acalabrutinib

BID=twice daily.

Table 2 Drug Modification and Discontinuation Actions for Acalabrutinib (Without

Lenalidomide)

Action
Hold acalabrutinib until recovery to Grade ≤1 or baseline; may restart at
original dose level (100 mg BID)
Hold acalabrutinib until recovery to Grade ≤1 or baseline; restart at 100 mg
once daily
Discontinue acalabrutinib

BID=twice daily.

Whenever possible, any dose adjustment of acalabrutinib should be discussed between the investigator and the Sponsor's medical monitor before implementation. The appropriate clinic staff should dispense the study drug for the new dose level and instruct the subject/caregiver about the change in dose level. Any changes to the dosing regimen must be recorded on the appropriate eCRF.

Rituximab dose modifications should follow the recommendations in the Rituxan/MabThera package insert and institutional standard practices.

Per the lenalidomide label, the dose adjustments listed in Table 3 are acceptable for lenalidomide.

Table 3 Dose Modification Actions for Lenalidomide

Toxicity	Dose Adjustment
Platelets <50 × 10 ⁹ /L:	Interrupt and follow CBC weekly
Platelets return to ≥50 × 10 ⁹ /L:	Resume at 5 mg less than previous dose. Discontinue if dose is reduced to <10 mg.
ANC <1.0 × 10 ⁹ /L × 7 days	Interrupt and follow CBC weekly
or ANC <1.0 × 10 ⁹ /L with an associated temperature ≥38.5°C	
or ANC <0.5 × 10 ⁹ /L:	
ANC returns to ≥1.0 × 10 ⁹ /L:	Resume at 5 mg less than previous dose. Discontinue if dose is reduced to <10 mg.
Other Grade 3/4 toxicities related to lenalidomide:	Hold treatment and restart at the investigator's discretion at the next lower dose when toxicity has resolved to ≤Grade 2

ANC=absolute neutrophil count; CBC=complete blood count.

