3.7.3 Risks Associated with Lenalidomide (Revlimid) Treatment

Cases of PML, including fatal cases, have been reported in subjects treated with lenalidomide in combination with immunosuppressive therapy including dexamethasone. Signs and symptoms of PML may include cognitive and behavioral changes, language disturbances, visual disturbances, sensory deficits, weakness, and coordination and gait difficulties. If PML is suspected, hold further treatment with lenalidomide until PML is excluded. If PML is confirmed, lenalidomide will be permanently discontinued.

For complete information refer to the local label Reference Safety Information for lenalidomide (Revlimid package insert) for this study. Also refer to Section 3.5.7 in this protocol for specific dose modification and discontinuation guidelines.

Contraindications

Pregnancy

Lenalidomide can cause fetal harm when administered to a pregnant female.

Lenalidomide is contraindicated in females who are pregnant per the package insert.

Allergic Reactions

Lenalidomide is contraindicated in patients who have demonstrated hypersensitivity (e.g., angioedema, Stevens-Johnson syndrome, toxic epidermal necrolysis) to lenalidomide.

Revlimid capsules contain lactose. The risk-benefit of Revlimid treatment should be evaluated in subjects with lactose intolerance per package insert.

Warnings and Precautions

Embryo-fetal Toxicity

If lenalidomide is used during pregnancy, it may cause birth defects or embryo-fetal death (boxed warning). Pregnancy must be excluded before start of treatment.

Hematologic Toxicity

Lenalidomide can cause significant neutropenia and thrombocytopenia (boxed warning).

Venous and Arterial Thromboembolism

Venous thromboembolic events (deep vein thrombosis and pulmonary embolism) and arterial thromboembolic events (myocardial infarction and stroke) are increased in patients treated with lenalidomide and seen in patients treated for multiple myeloma (boxed warning).

Mvocardial Infarction

Myocardial infarction has been reported in patients receiving lenalidomide, particularly in those with known risk factors and within the first 12 months when used in combination with dexamethasone. Patients with known risk factors – including prior thrombosis – should be closely monitored, and action should be taken to try to minimize all modifiable risk factors (eg. smoking, hypertension, and hyperlipidemia).

Increased Mortality

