Serious and fatal cardiac adverse reactions occurred in patients with CLL treated with lenalidomide.

Second Primary Malignancies

Higher incidences of second primary malignancies were observed in controlled trials of patients with multiple myeloma receiving lenalidomide.

Hepatotoxicity

Hepatic failure, including fatal cases, has occurred in patients treated with lenalidomide in combination with dexamethasone. Monitor liver enzymes as indicated in Section 4.1.12 and stop lenalidomide upon elevation of liver enzymes per the package insert.

Allergic Reactions

Angioedema and serious dermatologic reactions including Stevens-Johnson syndrome and toxic epidermal necrolysis have been reported. These events can be fatal. Discontinue lenalidomide if allergic reactions are suspected. Do not resume lenalidomide if these reactions are verified.

Tumor Lysis Syndrome

Fatal instances of TLS have been reported during treatment with lenalidomide. Monitor subjects at risk of TLS (i.e., those with high tumor burden) and take appropriate precautions per the package insert.

Tumor Flare Reaction

Tumor flare reaction has occurred during investigational use of lenalidomide for CLL and lymphoma and is characterized by tender lymph node swelling, low grade fever, pain, and rash. Tumor flare reaction may mimic progression of disease. Lenalidomide may be continued in patients with Grade 1 and Grade 2 tumor flare reaction without interruption or modification per the package insert.

Viral Reactivation Including Hepatitis B Reactivation

Serious or life-threatening reactivation of viral hepatitis may occur in subjects treated with lenalidomide ("Dear Health Care Provider letter November 2016").

Impaired Stem Cell Mobilization

A decrease in the number of CD34⁺ cells collected after treatment (>4 cycles) with lenalidomide has been reported.

Thyroid Disorders

Both hypothyroidism and hyperthyroidism have been reported.

Pulmonary hypertension

Cases of pulmonary hypertension, some fatal, have been reported in patients treated with lenalidomide. Patients should be evaluated for signs and symptoms of underlying cardiopulmonary disease prior to initiating and during lenalidomide therapy.

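### Protocol Table 3 permits lenalidomide to be restarted after a verified Grade 3/4 allergic or severe skin reaction, which Section 3.7.3 forbids, and no text says which section governs

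*Protocol*

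**What the plan says.** Protocol Section 3.5.7 introduces the lenalidomide rules with: "Per the lenalidomide label, the dose adjustments listed in Table 3 are acceptable for lenalidomide". Table 3 then has three parts.

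- **Platelet row and neutrophil row.** Interrupt, follow counts weekly, and on recovery: "Resume at 5 mg less than previous dose. Discontinue if dose is reduced to <10 mg".
- **Residual row.** It is labelled "Other Grade 3/4 toxicities related to lenalidomide", and its action is: "Hold treatment and restart at the investigator's discretion at the next lower dose when toxicity has resolved to ≤Grade 2". It names no excluded event, no step size and no minimum dose.

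Protocol Section 3.7.3 deals with the same drug under risks. Its contraindications include: "Lenalidomide is contraindicated in patients who have demonstrated hypersensitivity", with angioedema, Stevens-Johnson syndrome and toxic epidermal necrolysis as examples. Under warnings it states: "Angioedema and serious dermatologic reactions including Stevens-Johnson syndrome and toxic epidermal necrolysis have been reported". It adds that such events can be fatal, and then gives the instruction: "Discontinue lenalidomide if allergic reactions are suspected. Do not resume lenalidomide if these reactions are verified".

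Near its start, Section 3.7.3 points the reader to Section 3.5.7 for dose modification and discontinuation guidance. The lenalidomide text in Section 3.5.7 does not point back, and neither section states an order of precedence.

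**The concern.** Table 3 is where a site will look when it has to decide whether a subject goes back on lenalidomide. Read alone, its last row covers a related Grade 3 or 4 allergic or skin reaction and allows re-exposure once the reaction has eased. Section 3.7.3 bars re-exposure after the same reaction if it is verified. The protocol itself describes these reactions as potentially fatal, so this is a safety matter first.

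There is also a consequence for the analysis. Safety is the primary objective of Part 3. SAP Section 7.5.3 summarises lenalidomide relative dose intensity, withholding, reduction and the reasons for them. SAP Section 7.7.1 tabulates adverse events that lead to discontinuation, dose modification or delay. If sites resolve the conflict differently, the same clinical event falls into different tables and gives a different dose intensity. That difference would reflect the wording of the protocol and not the tolerability of the combination.

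**Working it through.** The plan gives no figure on this point to reproduce. The check is a comparison of texts, plus two pieces of hand arithmetic.

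**1. Does one event fall under both rules?** Take a reaction that meets all of these conditions:

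- it is Grade 3 or 4 and judged related to lenalidomide;
- it is not a platelet or neutrophil event;
- it is verified as angioedema, Stevens-Johnson syndrome, toxic epidermal necrolysis or another allergic reaction;
- it has improved to Grade 2 or less.

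| Source | What it says for this subject |
|---|---|
| Table 3, residual row | Restart at the next lower dose is open to the investigator |
| Section 3.7.3, allergic reactions | No resumption |
| Section 3.7.3, contraindications | Demonstrated hypersensitivity is a contraindication |
| Precedence between 3.5.7 and 3.7.3 | Not stated |

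The event satisfies every condition of the Table 3 row, and it is the event that Section 3.7.3 addresses. One section permits what the other forbids.

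**2. Does another section settle it?** Section 3.5.5 counts Stevens-Johnson syndrome or toxic epidermal necrolysis of any grade as a dose-limiting toxicity. That rule drives cohort decisions; it does not say whether the affected subject may be re-exposed. Confirmed progressive multifocal leukoencephalopathy shows the same drafting pattern: Section 3.7.3 requires a permanent stop, and Table 3 carries no such exception.

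**3. The dose step in the residual row.** The platelet and neutrophil rows use a 5-mg step and stop when the reduced dose is below 10 mg:

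- from 20 mg: 20 − 5 = 15; 15 − 5 = 10; 10 − 5 = 5, below 10, so the third reduction is a stop;
- from 15 mg: 15 − 5 = 10; 10 − 5 = 5, so the second is a stop;
- from 10 mg: 10 − 5 = 5, so the first is a stop.

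The residual row has no corresponding sequence. At 10 mg, a qualifying cytopenia ends lenalidomide, while another related Grade 3/4 toxicity may be followed by a restart at a dose the protocol does not name. Section 3.5.2 lists capsules of 5 mg and 2.5 mg, so supply does not settle the meaning. Subjects can be at 10 mg by reduction or by assignment. In the de-escalation branch of Section 3.1, if the first six subjects at 10 mg pass the toxicity review, about "14 additional subjects will be enrolled and treated with lenalidomide 10 mg QD for Cycles 1 through 12".

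**4. Effect on dose intensity (illustration only).** SAP Section 7.5.3 divides cumulative dose by planned dosing days between first and last dose, then by the assigned dose. Assume an assigned dose of 15 mg, all 21 doses of Cycle 1 taken, and a reaction at the end of that period.

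- Lenalidomide not resumed: cumulative dose 21 × 15 = 315 mg; duration 21 days; 21/28 rounds up to 1 cycle; planned days 21 − 7 × 0 = 21; average 315/21 = 15 mg; relative dose intensity 15/15 = 100%.
- Resumed on Cycle 2 Day 1 for 21 days at 10 mg (borrowing the 5-mg step of the cytopenia rows): cumulative dose 315 + 210 = 525 mg; duration 49 days; 49/28 = 1.75 rounds up to 2 cycles; planned days 49 − 7 × 1 = 42; average 525/42 = 12.5 mg; relative dose intensity 12.5/15 = 83.3%.

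The same reaction gives 100% or 83.3% according to which section the site applied.

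**The case against.** The strongest reply is that both passages can be obeyed. Table 3 does not order a restart: it leaves it to the investigator, and it is introduced as a set of acceptable adjustments. Section 3.7.3 is the more specific text, and its pointer to Section 3.5.7 adds a reference without giving that section priority. A site that does not restart complies with both; a site that re-exposes a verified case breaches Section 3.7.3. This stands, and it limits the point to a general permission without the exception that a specific prohibition needs. It does not remove the point, because a site working from Table 3 has no prompt to look for that prohibition.

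Several stronger readings are tempting but not supported:

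- **That sites have instructions which cannot both be followed.** The discretion in Table 3 rules this out.
- **That the row covers every related Grade 3/4 toxicity.** It covers those left over after the platelet and neutrophil rows.
- **That a suspected allergic reaction of Grade 1 or 2 is a second conflict.** Table 3 is silent on it, so Section 3.7.3 applies alone wherever it applies.
- **That the stop below 10 mg contradicts the residual row.** Different toxicities may have different minimum doses. What remains is an undefined term.
- **That most Part 3 subjects are exposed to the conflict, because rash occurred in 82% on the ibrutinib triplet cited in Sections 1.7 and 3.3.** That figure is rash of any grade, with another BTK inhibitor, in previously untreated follicular lymphoma; Part 3 enrols relapsed or refractory disease. The share that was both Grade 3/4 and allergic is not given.
- **That a whole cohort was assigned 10 mg.** This needs the de-escalation branch to have opened. The SAP's dose-intensity formula names only 15 or 20 mg as assigned doses, which suggests, without proving, that it did not.

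**Conclusion.** The point holds in a narrow form. For a verified, lenalidomide-related Grade 3/4 allergic or severe skin reaction that has improved to Grade 2 or less, Table 3 permits a restart that Section 3.7.3 forbids, and the protocol does not say which governs. The passages must be reconciled. This rests on reading the residual row literally and on finding no precedence rule in either section. It implies no view on which clinical rule is right and no claim that any subject was harmed.

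The number of subjects affected cannot be derived from the documents. For the analysis, the consequence is confined to the Part 3 lenalidomide exposure and discontinuation summaries.

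The missing step and minimum dose in the residual row are a separate, lesser ambiguity, felt most at 10 mg. Lenalidomide is limited to 12 cycles, and the documents do not say whether anyone still takes it. If nobody does, what remains is to report how such cases were handled.

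**What to change.** At the next amendment, add to the residual row of Table 3 a cross-reference to Section 3.7.3 and a statement of which section governs allergic and severe dermatologic reactions. The sponsor's clinical team decides the content.

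Separately, ask the sponsor to clarify what the next lower dose means in that row, including for a subject already at 10 mg. No particular step or minimum is proposed here.

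If no subject remains on lenalidomide, state instead in the clinical study report for Parts 2 and 3 how any such reactions were handled and how they were classified in the exposure and discontinuation tables.

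The cost is a few sentences of protocol or report text. No new data, patients or analyses are needed.
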